2.1.3 Propensity Score

Given that subjects in the two comparison groups (the 1-month DAPT arm vs XIENCE V USA historical control) are not randomized and thus may not have balanced baseline characteristics, the non-inferiority and superiority tests for 1-6 month period will be carried out through stratified analysis in the “1-month clear” population. The stratification will be performed through propensity scores (PS). For each individual a propensity score (i.e., predicted probability between 0 and 1) for group (1-month DAPT arm) membership will be calculated using logistics regression, with “group” as the outcome and baseline variables including demographic, lesion characteristics, and risk factors as the predictors. Subjects will be categorized into 5 groups based on the calculated propensity scores and their quintiles. Non-inferiority and superiority will then be carried out for the rate of the endpoint using the method described in sections below stratified by the propensity quintiles.

The propensity score modeling and design will be performed by an independent statistician who has no access to any outcome data of the XIENCE 28 Global study and the XIENCE V USA historical control for the integrity and interpretability of study results. The independent statistician will be blinded and have no access to clinical outcome and any follow-up information to avoid introducing bias into the analysis. [REDACTED]

2.1.3-1 Propensity Score Variable List

Based on prior clinical experience and clinical research, below is the list of variables that are considered to be related to assignments modeling building:

- Gender
- Age
- Creatinine
- Chronic anticoagulant
- History of stroke
- History of major bleeding
- Platelet
- Hb
- BMI
- Hypertension
- Dyslipidemia
- Prior PCI
- Prior CABG
- Prior MI
- Multivessel disease
- Clinical presentation (ACS (NSTEMI, ACS unstable angina) vs. non-ACS)
- Diabetes
- ACC/AHA lesion complexity

- Total lesion length per patient
- RVD
- Diameter stenosis%
- Bifurcation
- Number of lesions treated
- Number of vessels treated
- Number of stents per patient
- Total stent length per patient
- Discharge P2Y12
- Paris bleeding score
- PRECISE DAPT score

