4. Subject is willing to comply with all protocol requirements, including agreement to stop taking P2Y12 inhibitor at 1 month, if eligible per protocol.
5. Subject must agree not to participate in any other clinical trial for a period of one year following the index procedure.

Angiographic Inclusion Criteria

1. Up to three target lesions with a maximum of two target lesions per epicardial vessel. Note:
 - The definition of epicardial vessels means left anterior descending coronary artery (LAD), left circumflex coronary artery (LCX) and right coronary artery (RCA) and their branches. For example, the subject must not have >2 lesions requiring treatment within both the LAD and a diagonal branch in total.
 - If there are two target lesions within the same epicardial vessel, the two target lesions must be at least 15 mm apart per visual estimation; otherwise this is considered as a single target lesion.
2. Target lesion must be located in a native coronary artery with visually estimated reference vessel diameter between 2.25 mm and 4.25 mm.
3. Exclusive use of XIENCE family of stent systems during the index procedure.
4. Target lesion has been treated successfully, which is defined as achievement of a final in-stent residual diameter stenosis of <20% with final TIMI-3 flow assessed by online quantitative angiography or visual estimation, with no residual dissection NHLBI grade ≥ type B, and no transient or sustained angiographic complications (e.g., distal embolization, side branch closure), no chest pain lasting > 5 minutes, and no ST segment elevation > 0.5mm or depression lasting > 5 minutes.

PROTOCOL ABT-CIP-10398 XIENCE 28 Global Study

Key Exclusion Criteria

General Exclusion Criteria

1. Subject with an indication for the index procedure of acute ST-segment elevation MI (STEMI).
2. Subject has a known hypersensitivity or contraindication to aspirin, heparin/bivalirudin, P2Y12 inhibitors (clopidogrel/prasugrel/ticagrelor), everolimus, cobalt, chromium, nickel, tungsten, acrylic and fluoro polymers or contrast sensitivity that cannot be adequately pre-medicated.
3. Subject with implantation of another drug-eluting stent (other than XIENCE) within 12 months prior to index procedure.
4. Subject has a known left ventricular ejection fraction (LVEF) <30%.
5. Subject judged by physician as inappropriate for discontinuation from P2Y12 inhibitor use at 1 month, due to another condition requiring chronic P2Y12 inhibitor use.

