5.3.1.2 General Exclusion Criteria

1. Subject with an indication for the index procedure of acute ST-segment elevation MI (STEMI).
2. Subject has a known hypersensitivity or contraindication to aspirin, heparin/bivalirudin, P2Y12 inhibitors (clopidogrel/prasugrel/ticagrelor), everolimus, cobalt, chromium, nickel, tungsten, acrylic and fluoro polymers or contrast sensitivity that cannot be adequately pre-medicated.
3. Subject with implantation of another drug-eluting stent (other than XIENCE) within 12 months prior to index procedure.
4. Subject has a known left ventricular ejection fraction (LVEF) $<30\%$.

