6.1.2 Clinical Assessments

Subject demographics (age, gender, race), height, weight, family history of coronary artery disease (CAD), smoking status, cardiac history (myocardial infarction, diabetes mellitus, hypertension, hypercholesterolemia, and previous PCI/CABG information), subject's current cardiac status (presentation of CAD and multivessel disease) and indication of high bleeding risk (per criteria specified in **Section 5.3.1.1**) will be obtained and recorded in electronic case report form (eCRF).

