2.7 Adjustments for Covariates

Unless otherwise specified, no adjustments for covariates will be made for any of the variables in the analyses.

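### The visible propensity list omits smoking status, which the trial records at baseline, without a stated reason; this leaves possible residual confounding, in either direction, in the primary comparison

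*SAP*

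**What the plan says.** SAP 2.1.3 acknowledges that the two groups are not randomized and may differ at baseline. It fits a logistic model for group membership with "baseline variables including demographic, lesion characteristics, and risk factors as the predictors", cuts the score into quintiles and stratifies the primary test on them. SAP 2.1.3-1 then gives the covariates: "below is the list of variables that are considered to be related to assignments modeling building". The visible list has 29 entries. It includes hypertension, dyslipidemia, diabetes, prior MI, clinical presentation, multivessel disease, the "Paris bleeding score" and the PRECISE DAPT score. Neither smoking status nor LVEF is named.

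Protocol 6.1.2 lists what is recorded in the eCRF at baseline, including "family history of coronary artery disease (CAD), smoking status, cardiac history" and, within that history, diabetes, hypertension and hypercholesterolemia.

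LVEF appears only as a selection criterion. Protocol 5.3.1.2 excludes a subject under the criterion "Subject has a known left ventricular ejection fraction (LVEF" with the limit set at below 30%. SAP 1.3.1 applies an LVEF cut at 30% to the control as well.

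Outside the propensity score, SAP 2.7 states: "Unless otherwise specified, no adjustments for covariates will be made for any of the variables in the analyses".

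**The concern.** A propensity score balances the variables in the model and, beyond those, only what is correlated with them. The trial is global and the control is a US post-approval registry of an earlier XIENCE stent, so equal smoking prevalence cannot be presumed. NACE includes death, MI, stent thrombosis and stroke as well as bleeding, and a prognostic effect of smoking on such a composite is plausible, though the documents do not quantify it.

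The omission is conspicuous because the neighbouring risk factors collected in the same paragraph were kept. Nothing else in the visible plan would reveal an imbalance. The quartile analysis in SAP 2.2.1 changes only the cut-points, and SAP 2.9 deals with medication compliance and missing outcomes. What is at stake is a shift in the estimated NACE difference that the test against the 4.0-point margin would read as part of the treatment comparison.

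**Working it through.** **1. The list against the data collected**

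| Protocol 6.1.2 baseline item | In SAP 2.1.3-1? |
|---|---|
| Diabetes mellitus | Yes |
| Hypertension | Yes |
| Hypercholesterolemia | Yes, as dyslipidemia |
| Smoking status | No |
| LVEF (not an item in 6.1.2) | No |

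**2. Inputs**

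- From the documents: margin 4.0 points and one-sided alpha 0.05 (SAP 2.1.4); about 800 trial subjects and about 1,400 controls (SAP 1.5).
- Assumed, because no values are visible: the NACE rate, the risk ratio (RR) for smoking, and the prevalence in each group. Smoking is also assumed independent of all 29 listed covariates, so none of the imbalance is removed by the stratification.

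The plan has no figure for this bias to reproduce. The 800 cannot be re-derived either, since the assumed rates and power are not visible.

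**3. Size of the bias**

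Two forms were used, both at 10% NACE. With trial prevalence pt and control prevalence pc:

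- Ratio form, taking 10% as the overall control rate: bias = 10 × {[1 + (RR − 1)pt] / [1 + (RR − 1)pc] − 1} points.
  - RR 1.5, pt 10%, pc 20%: 10 × (1.05/1.10 − 1) = −0.45 points, favouring the trial arm.
  - RR 1.5, pt 20%, pc 10%: 10 × (1.10/1.05 − 1) = +0.48 points, against the trial arm.
- Additive form, taking 10% as the rate in subjects without the factor: 0.10 × (1.5 − 1) × 0.10 = 0.005, or 0.5 points in whichever direction the gap runs.

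So 0.45–0.5 points is about 11–12.5% of the margin (0.45/4.0 and 0.5/4.0).

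Range in the ratio form with the control prevalence higher: from 0.14 points (RR 1.3, 15% vs 20%: 10 × (1 − 1.045/1.06)) to 0.83 points (RR 2.0, 10% vs 20%: 10 × (1 − 1.10/1.20)). With the two groups exchanged, the upper figure is 0.91 points (10 × (1.20/1.10 − 1)).

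**4. Effect on the test at the margin**

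Control rate 10%, trial rate 14%, simple unpooled standard error:

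SE = √(0.14 × 0.86/800 + 0.10 × 0.90/1,400) = 1.47 points.

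Type I error = Φ(b/SE − 1.645), with b positive when the bias favours the trial arm:

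| b (points) | One-sided type I error |
|---|---|
| 0 | 5.0% |
| +0.4 | 8.5% |
| +0.45 | 9.0% |
| +0.5 | 9.6% |
| −0.48 | 2.4% |

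At the ends of the range, b = 0.14 gives about 6% and b = 0.83 about 14%.

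**5. Cost of the reverse direction**

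If both true rates are 10%, SE = √(0.10 × 0.90 × (1/800 + 1/1,400)) = 1.33 points, and power is Φ(4.0/1.33 − 1.645) = 91.4%. A 0.48-point bias against the trial arm lowers this to Φ(3.52/1.33 − 1.645) = about 84%.

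These are normal approximations without strata. The planned stratified Farrington-Manning test would give somewhat different values.

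**The case against.** The best reply is that the list is prespecified on clinical grounds and already long, and that an independent statistician without access to outcomes builds the model. Any list of 29 can be asked for a 30th. Four specific points follow, and each has some force.

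- **No imbalance is shown.** A reader might infer that known prognostic differences from the registry go unadjusted. The documents do not support that: they give neither smoking nor LVEF distributions for either group, and no association of either with NACE. This stands, and the point is limited to possible confounding.
- **Smoking may be partly covered.** Two composite bleeding scores are listed and the documents do not give their components. Age, prior MI, clinical presentation and other entries may also carry some of the information. This stands as a reason why the true bias could be smaller than calculated. It does not remove the point, because balance on a total score does not guarantee balance on each component.
- **Control availability is unstated.** The documents do not say that the XIENCE V USA data hold smoking status. This stands and makes the remedy conditional.
- **LVEF is different.** A reader might infer from the shared exclusion that LVEF is already recorded in both groups and costs nothing to add. It is not among the items in Protocol 6.1.2, and only a known low value excludes, so a subject without a measurement can enter. The common cut at 30% also removes the low end from both groups.

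Part of the propensity section is redacted, so the visible text may not be the whole design.

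**Conclusion.** The point holds for smoking status, as a gap worth closing rather than a demonstrated bias. The trial collects the variable, the visible list omits it without explanation, and neither another adjustment nor a visible sensitivity analysis would compensate. The illustrative size is about 0.45–0.5 NACE points. For shifts of 0.4–0.5 points favouring the trial arm, type I error at the margin is roughly 8.5–9.6% instead of 5%. In the reverse direction the test is conservative and loses power.

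This rests on an assumed 10% NACE rate, risk ratio 1.5 and 10-point prevalence gap, and on independence from the listed covariates. None of these comes from the documents, and only imbalance remaining within quintiles would matter. For LVEF the documents support no more than a conditional suggestion about its distribution at or above 30%.

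**What to change.** Before the propensity model is built:

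1. Add smoking status to SAP 2.1.3-1 if the XIENCE V USA data hold it, with missing values handled by the multiple imputation in SAP 2.5.
2. If the control lacks it, say so in the SAP and report the trial-arm distribution.
3. For LVEF, first check how completely it is recorded in each data set. If recording is adequate in both, report its balance within quintiles and include it in a sensitivity propensity model. If it is largely unrecorded in one source, do not rely on imputation to supply it.

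The cost is a few lines in the SAP and one covariate in the primary model, plus one in a sensitivity model, against about 800 and 1,400 subjects. Smoking needs no new collection in the trial. The real limit is what the control data contain. Because the modelling statistician is blinded to outcomes, a change made at this stage does not compromise the design.

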2.1.4 Hypothesis Testing

Primary endpoint analysis for 1-month DAPT

[figure not shown]
The XIENCE 28 Global study is powered based on primary endpoint of NACE between 1-month and 6-month follow-up. NACE is defined as the composite rate of all-cause death, all myocardial infarction (modified Academic Research Consortium [ARC]), stent thrombosis (ARC definite or probable), stroke or major bleeding (Bleeding defined by the Bleeding Academic Research Consortium [BARC] type 2-5) from 1 to 6 months. This primary endpoint will be evaluated between 1-month DAPT arm and XIENCE V USA historical control stratified by propensity score quintiles in the primary analysis population. The null (H_0) and alternative (H_A) hypothesis are of the following form:

$$H_0: NACE_{1m-DAPT} - NACE_{Xience\ V\ USA} \geq \delta$$

$$H_A: NACE_{1m-DAPT} - NACE_{Xience\ V\ USA} < \delta$$

Where δ is the non-inferiority margin. The test will be carried out with a one-sided significance level of 0.05 and a non-inferiority margin (δ) of 4.0%.

The stratified Farrington-Manning method will be performed to test non-inferiority (NI) of 1-month DAPT compared to standard DAPT duration from XIENCE V USA historical control.

[REDACTED]

[REDACTED]

[REDACTED]

[REDACTED]

[REDACTED]

2.1.5 Survival Analyses

Survival analysis may be conducted to analyze time-to-event variables. Subjects without events will be censored at their last known event-free time point. Survival curves will be constructed using Kaplan-Meier estimates.

Summary tables for the endpoints will include failure rates (Kaplan-Meier estimates). For the primary analysis report, all available data will be used.

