9.4 Statistical Analyses

A stratified statistical method through propensity score will be used to test non-inferiority of 1-month DAPT to XIENCE V USA historical control at a 0.05 significant level.

Analyses of other secondary endpoints and additional endpoints will be descriptive in nature.

For binary variables such as TLR, TVR, counts, percentages and 95% confidence intervals will be calculated, and p-values may be presented for hypothesis generating purposes. Pearson’s Chi-squared test of Fisher’s exact test will be performed when appropriate.

For continuous variables such as age, means, standard deviation, and 95% confidence intervals for the mean will be calculated and p-values may be presented for hypothesis generating purposes. For time-to-event variables, such as time to Death/MI, survival curves will be constructed using Kaplan-Meier estimates, and log rank test results will be displayed. Unless specified, analyses will be performed with pooled data across all trial sites.

For further details refer to the Statistical Analysis Plan (SAP).

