1.3.3 Secondary Endpoint(s)

The following endpoints will be assessed from 1 to 6 months:

- Stent thrombosis (ARC definite/probable, ARC definite)
- All death, cardiac death, vascular death, non-cardiovascular death
- All myocardial infarction (MI) and MI attributed to target vessel (TV-MI, modified ARC)
- Composite of cardiac death or MI (modified ARC)
- Composite of all death or all MI (modified ARC)
- All stroke, ischemic stroke and hemorrhagic stroke
- Clinically-indicated target lesion revascularization (CI-TLR)
- Clinically-indicated target vessel revascularization (CI-TVR)
- Target lesion failure (TLF, composite of cardiac death, TV-MI and CI-TLR)
- Target vessel failure (TVF, composite of cardiac death, TV-MI and CI-TVR)
- Bleeding defined by the Bleeding Academic Research Consortium (BARC) type 2-5 and type 3-5

The primary endpoints of NACE and all the above secondary endpoints will also be assessed from 6 months to 12 months and from 1 month to 12 months, respectively.

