2.1.2 Descriptive Statistics for Categorical Variables

For categorical variables such as gender, NACE and TLF, results will be summarized with subject counts and percentages/rates, [REDACTED] with exact two-sided 95% Clopper-Pearson⁶ confidence intervals. Differences between two comparison groups of interest, when specified, will be summarized with the difference in percentages and the Newcombe⁵ score two-sided 95% confidence interval for the difference of two percentages.

For efficacy and safety endpoint(s), relative risks (i.e., the ratio of rates), confidence interval for the relative risks, the difference in rates and the confidence interval for difference in rates (using previously-described formulas), and p-values may also be presented for hypothesis generating purposes. The p-values will be based on either Pearson's Chi-square test or Fisher's exact test by checking the expected frequency for each cell in the 2x2 contingency table against Cochran's rule⁸, i.e., if the expected frequencies for all cells are ≥ 5 , then Pearson's Chi-square test will be used, otherwise Fisher's exact test will be used.

[REDACTED]

[REDACTED]

[REDACTED]

[REDACTED]

[REDACTED]

[REDACTED]

[REDACTED]

[REDACTED]

[REDACTED]

[REDACTED]

[REDACTED]

Formulas for calculating confidence intervals for the categorical variables are given below.

1. 100(1- α) % Exact Clopper-Pearson Confidence Interval for A Single Proportion⁶

$$\text{Lower Confidence Limit} = \frac{x}{x + (n - x + 1)F_{1-\frac{\alpha}{2}}(2(n - x + 1), 2x)}$$

$$\text{Upper Confidence Limit} = \frac{(x + 1)F_{1-\frac{\alpha}{2}}(2(x + 1), 2(n - x))}{n - x + (x + 1)F_{1-\frac{\alpha}{2}}(2(x + 1), 2(n - x))}$$

where:

n = sample size

x = number of "events"

$F_{1-\frac{\alpha}{2}}(df_1, df_2)$ = the (1- α /2) F - statistic for degrees of freedom df_1 and df_2

2. 100(1- α) % Newcombe Score Confidence Interval for the Difference of Two Proportions⁷

a. 100(1- α) % Wilson Score Confidence Interval for A Single Proportion⁵

$$\text{Lower Confidence Limit} = \left(\hat{p} + Z_{\alpha/2}^2 / 2n - Z_{\alpha/2} \sqrt{(\hat{p}(1 - \hat{p}) + Z_{\alpha/2}^2 / 4n) / n} \right) / (1 + Z_{\alpha/2}^2 / n)$$

$$\text{Upper Confidence Limit} = \left(\hat{p} + Z_{\alpha/2}^2 / 2n + Z_{\alpha/2} \sqrt{(\hat{p}(1 - \hat{p}) + Z_{\alpha/2}^2 / 4n) / n} \right) / (1 + Z_{\alpha/2}^2 / n)$$

where:

$$\hat{p} = x / n$$

n = sample size

x = number of "events"

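### Kaplan-Meier failure rates for endpoints that exclude all-cause death would modestly overstate those rates; cumulative incidence is a cheap improvement

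*SAP*

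**What the plan says.** SAP 2.1.5 opens permissively: "Survival analysis may be conducted to analyze time-to-event variables". Its next rule is general: "Subjects without events will be censored at their last known event-free time point". The reporting sentence is not optional and does not separate one endpoint from another: "Summary tables for the endpoints will include failure rates (Kaplan-Meier estimates". Protocol 9.4 also plans Kaplan-Meier for time-to-event variables: "survival curves will be constructed using Kaplan-Meier estimates, and log rank test results will be displayed". Its example there, time to Death/MI, is one in which death is an event.

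The endpoints in SAP 1.3.3 are of three kinds:
- Those that include all-cause death: NACE, all death, and all death or all MI.
- Those that include some deaths, for example "Target lesion failure (TLF, composite of cardiac death, TV-MI and CI-TLR". TVF and cardiac death or MI likewise count only cardiac death, and BARC 2-5 and 3-5 bleeding count only fatal bleeding.
- Those that count no deaths as such (stent thrombosis, MI, stroke, CI-TLR, CI-TVR), and the separate causes in "All death, cardiac death, vascular death, non-cardiovascular death".

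A second kind of rate is also planned. SAP 2.1.2 says "For categorical variables such as gender, NACE and TLF, results will be summarized with subject counts and percentages/rates", with exact confidence intervals. Protocol 9.4 says "For binary variables such as TLR, TVR, counts, percentages and 95% confidence intervals will be calculated". No readable text treats death as a competing event, plans a cumulative incidence function, or says which of the two rates is the main one for an endpoint.

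**The concern.** A patient who dies without a stent thrombosis is, for that endpoint, a subject without the event. Under the stated rule the patient is censored around the date of death and handled like someone who left follow-up alive and could still have the event. One minus Kaplan-Meier then estimates a risk in a setting where nobody dies of anything else. It does not estimate the proportion of patients who have the event, which is how readers will take a failure rate in a summary table.

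Two things follow. The Kaplan-Meier rate lies above the true incidence by an amount that grows with the mortality that is censored. If mortality differs between the trial and the XIENCE V USA control, the excess also differs between the two columns. Second, the three cause-specific death rates need not add up to the all-death rate shown beside them. At stake is the accuracy of the secondary-endpoint tables, which SAP 2.2.3 describes as descriptive.

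**Working it through.** **Figures in the plan.** The documents state no Kaplan-Meier, cumulative incidence or mortality figure for this point, so there is nothing to reproduce. Mortality over the window is assumed to lie between 2% and 15%. The figure of about 800 subjects (SAP 1.5) is used only to turn points into patients.

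**Model.** Constant hazards over the window.
- Competing mortality D gives a death hazard d = -ln(1 - D).
- An event hazard h gives 1-KM = 1 - exp(-h).
- The true cumulative incidence is C = h/(h + d) × [1 - exp(-(h + d))].

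**Check 1: fix the Kaplan-Meier rate at 10%**, so h = -ln(0.90) = 0.1054.
- D = 5%: d = 0.0513, C = 0.1054/0.1567 × 0.1450 = 9.75%
- D = 8%: d = 0.0834, C = 0.1054/0.1887 × 0.1720 = 9.60%
- D = 15%: d = 0.1625, C = 0.1054/0.2679 × 0.2350 = 9.24%

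**Check 2: fix the true incidence at 5% and solve for h.** Example, D = 5%: h = 0.05264 gives C = 0.05264/0.10393 × 0.09871 = 5.00%, and 1-KM = 1 - exp(-0.05264) = 5.13%.

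| Assumed D | True incidence | 1-KM | Excess, points | Relative excess | Patients in 800 |
|---|---|---|---|---|---|
| 2% | 5% | 5.05% | 0.05 | 1.0% | 0.4 |
| 3% | 5% | 5.08% | 0.08 | 1.5% | 0.6 |
| 5% | 5% | 5.13% | 0.13 | 2.6% | 1.0 |
| 8% | 5% | 5.21% | 0.21 | 4.2% | 1.7 |
| 10% | 5% | 5.27% | 0.27 | 5.3% | 2.2 |
| 15% | 5% | 5.41% | 0.41 | 8.3% | 3.3 |

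The relative excess is nearly the same for true incidences from 0.5% to 10%. A 2% endpoint at D = 5% is therefore overstated by about 0.05 points.

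**Scale against sampling error.** For a 5% rate in 800 patients the standard error is sqrt(0.05 × 0.95/800) = 0.77 points. An excess of 0.13 points is about 0.17 of a standard error, and 0.27 points about 0.35.

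**Check 3: do causes of death add up?** Assume deaths split 50/10/40 into cardiac, vascular and non-cardiovascular. At D = 5%, the rates 1 - exp(-share × 0.0513) are 2.53%, 0.51% and 2.03%, which sum to 5.07% before rounding. The three survival probabilities multiply to 0.95, so the three rates sum to more than D whenever at least two causes occur.

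| Assumed all-cause D | Sum of three KM rates |
|---|---|
| 2% | 2.01% |
| 5% | 5.07% |
| 8% | 8.19% |
| 10% | 10.31% |
| 15% | 15.71% |

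An equal three-way split gives a similar excess: 0.09 points at 5%, 0.35 at 10% and 0.82 at 15%. With cumulative incidence the three causes add up exactly.

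**Where all-cause mortality is the wrong D.** For TLF, TVF, cardiac death or MI, and bleeding, only the deaths that the endpoint leaves out compete. Protocol Appendix II classes a death as cardiac unless a non-cardiac cause is clearly established, so D for the first three is below all-cause mortality and the excess is smaller.

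**The case against.** The case against is substantial, and most of it limits the size of the point.

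- **Kaplan-Meier is not the only rate planned.** A reader might infer that every reported component rate is overstated. The documents do not support that: counts and crude percentages are also planned, do not censor deaths, and add up across causes.
- **A reader might infer a high-mortality population.** The eligibility criteria select older and sicker patients, but no document gives a mortality figure. Life expectancy under 12 months, STEMI and LVEF below 30% are excluded, and the primary window runs only from 1 to 6 months. The 15% row is an upper bound without a source.
- **A reader might infer distorted trial-versus-control testing.** The p-values in SAP 2.1.2 come from Pearson or Fisher tests on counts. The log-rank test in Protocol 9.4 compares cause-specific hazards, for which censoring other deaths is legitimate. The secondary endpoints are also compared without propensity stratification, and baseline imbalance may well matter more than differential mortality.
- **Censoring at death is inferred.** The SAP does not state it. Parts of the SAP are redacted, although no redaction shows in 2.1.5 itself.

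What stands on the other side is that the tables will carry Kaplan-Meier rates, the rule as written leaves death no other place than censoring, and no main rate is named. One endpoint could therefore appear with two different rates and no guidance on which to quote.

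**Conclusion.** The point holds as a minor one. As SAP 2.1.5 reads, the Kaplan-Meier rate for any endpoint that excludes all-cause death is biased upward as an estimate of the share of patients with the event. The relative excess is about 1% to 5% for assumed mortality of 2% to 10%, which on a 5% endpoint is 0.05 to 0.27 points. It is less where cardiac or fatal-bleeding deaths count as events. Cause-specific death rates can exceed all death by 0.01 to 0.09 points at 2% to 5% mortality and by 0.31 to 0.35 points at 10%. These sizes rest on constant hazards, assumed mortality and an assumed split of causes.

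The point does not reach the trial's conclusion. NACE, all death, and all death or all MI count every death as an event. The primary test is a stratified Farrington-Manning test on NACE, and SAP 1.6 ties success to that test alone.

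**What to change.** Add to SAP 2.1.5: *For endpoints that do not include all-cause death, deaths not counted in the endpoint are competing events, and failure rates are Aalen-Johansen cumulative incidence estimates. For NACE, all death, and all death or all MI, failure rates remain Kaplan-Meier estimates.*

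The competing deaths should be listed by endpoint:
- all deaths, for stent thrombosis, MI, stroke, CI-TLR and CI-TVR;
- deaths from other causes, for each cause of death;
- vascular and non-cardiovascular deaths, for TLF, TVF and cardiac death or MI;
- deaths not due to bleeding, for the BARC endpoints.

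If the sponsor prefers not to add an estimator, the minimum is to state how death is handled and to name the crude percentage as the main descriptive rate. Cumulative incidence is the better choice because it also allows for incomplete follow-up.

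The cost is a short SAP edit and a standard procedure option. SAP 2.10 sets only a minimum SAS version, so the release in use should be checked for it. Reported rates for these endpoints will be slightly lower. No new data are needed, and the log-rank comparisons and primary analysis stay as planned.
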